## **Eligibility criteria**

Inclusion criteria: Be male or female aged between 65 and 75 years old; Do not practice regular physical exercises for at least three months; No history of competitive sports throughout life; Not having musculoskeletal and neurological diseases or disorders that may influence the performance of the exercises or affect the test results; Not having health conditions in which physical exercise is contraindicated; Achieve a score of no less than 24 on the Mini Mental State Exam; Achieve a score of up to 9.11 on the Baecke Physical Activity Questionnaire.

Exclusion criteria: Miss more than 20% of training sessions; Miss more than three workouts in a row; Failure to attend any of the evaluations will be excluded from the study.

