## **Experimental design**

Initially, an interview will be carried out via telephone (or in person for volunteers who do not have access to this means of communication), in which clarifications about the study will be carried out, as well as scheduling of the first visit. The first face-to-face visit will take place at the University, in which the participants will be introduced to the responsible research subjects, will receive the informed consent form and, if they agree with all the study procedures, will be invited to sign the term in two copies. In case of acceptance, the tests referring to the inclusion criteria will be applied (Baecke's Physical Activity Questionnaire, Mini Mental State Examination and Geriatric Depression Scale), as well the socioeconomic and quality of life questionnaires. If the volunteers reach the required score, respectively below 9.11 and above 24, the second visit will be scheduled. On the second visit, blood collection will be performed to assess the lipid profile.

Afterwards, the subjects will be scheduled for the third visit, in which the quadriceps muscle thickness and quality assessment, anthropometric assessments, as well as familiarization with the lower limb strength test will be performed. Physical tests will be performed on the fourth visit. After the evaluations, the participants will be randomly allocated to one of the two interventions or the control group. After 8 weeks,

a fifth visit will be held, where the physical tests will be reassessed, as well as the application of the questionnaire on affectivity with the intervention. At the end of the 12 weeks of training, participants will be reassessed on all tests.

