## **STATISTICAL TREATMENT**

Results will be presented as mean  $\pm$  standard deviation. The distribution of normality and homogeneity parameters will be verified using the Shapiro-Wilk and Levene test respectively. Comparison of pre-training values between groups will be analyzed using one-way Analysis of Variance (ANOVA), regardless of data distribution, as ANOVA is robust enough for this (Sawyers, 2013). The effects of training will be evaluated using two-way ANOVA (time x group). If time x group interaction is observed, an analysis will be performed using one-way ANOVA with Tukey's post hoc test for group factor and repeated measures ANOVA for time factor. Significance will be accepted when  $p \leq 0.05$ . All statistical analyzes will be performed using SPSS software (version 25.0). The eta-square values will be used to analyze the effect size: small ( $\eta^2 \geq 0.02$ ), medium ( $\eta^2 \geq 0.13$ ) or large effect size ( $\eta^2 \geq 0.26$ ) (COHEN, 1988). Individuals who do not complete the study will be analyzed using intention to treat. All assessments and data analysis will be performed by researchers blinded to the group of participants.

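### Intention to treat is promised for non-completers, but no missing-data method is given, and the exclusion rules, read literally, remove randomised participants

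*Combined protocol and SAP*

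**What the plan says.** Under Statistical Treatment, the protocol states: "Individuals who do not complete the study will be analyzed using intention to treat". The main analysis is given as "The effects of training will be evaluated using two-way ANOVA (time x group"). If an interaction is seen, it is followed by "one-way ANOVA with Tukey's post hoc test for group factor and repeated measures ANOVA for time factor". No imputation rule, model for incomplete data, missing-data assumption or sensitivity analysis appears anywhere.

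Under Eligibility criteria, the exclusions are "Miss more than 20% of training sessions; Miss more than three workouts in a row", followed by "Failure to attend any of the evaluations will be excluded from the study". The text does not say whether exclusion means stopping training, stopping follow-up or removal from the analysis.

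Experimental design fixes the order of events. Baseline testing comes first, then allocation: "After the evaluations, the participants will be randomly allocated to one of the two interventions or the control group". At week 8, "a fifth visit will be held, where the physical tests will be reassessed", and then "At the end of the 12 weeks of training, participants will be reassessed on all tests". Physical tests therefore have three time points. Outcomes such as lipid profile, quality of life, cognition and depressive symptoms have only baseline and week 12.

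Under Arms and Interventions, traditional concurrent training has two sessions a week for 12 weeks, and controls keep their usual routine.

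**The concern.** Intention to treat settles who belongs in the comparison. It does not say what to do when an outcome is absent. People who do not complete the study are those most likely to lack week-8 or week-12 values, and a standard repeated-measures ANOVA leaves them out unless something is done about those values. As written, the promise has no means of being kept.

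The exclusion rules add a second problem. Nobody can miss training sessions before being allocated to training, so the session rules act only after randomisation. Controls have no sessions, so these rules can never remove a control. The evaluation rule also acts after randomisation at weeks 8 and 12, although not at the baseline visits. If the rules define the analysis set, a result labelled intention to treat would rest on a subset of those randomised, selected by attendance in two arms and not in the third. It would also leave out low attenders who came to every evaluation and have complete data.

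**Working it through.** **The passages side by side.** Someone who misses week 12 is excluded under Eligibility criteria and analysed under Statistical Treatment. Someone who misses five sessions but attends every evaluation is excluded despite having full data. No section reconciles these.

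**When the session rules bite.** Sessions: 2 × 12 = 24 (stated for the traditional arm; assumed the same for the dance arm). 20% of 24 = 4.8, so the fifth missed session triggers exclusion, as does a run of four.

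**How often.** The documents give no attendance rate, so the chance p of missing each session is assumed. With independent misses, follow the state (number missed m, current run r) over 24 sessions. A miss moves it to (m+1, r+1), attendance moves it to (m, 0), and exclusion occurs at m = 5 or r = 4. At p = 0.10 the count rule alone gives 1 − Σ(k=0..4) C(24,k) 0.1^k 0.9^(24−k) = 0.0851. Adding the run rule gives 0.0853.

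| Assumed p | Excluded, independent misses | Expected of 12 per exercise arm | Excluded if attendance varies between people* | Controls |
|---|---|---|---|---|
| 5% | 0.6% | 0.1 | 5–9% | 0 |
| 10% | 8.5% | 1.0 | 16–20% | 0 |
| 15% | 28.7% | 3.4 | 31–32% | 0 |
| 20% | 54.1% | 6.5 | 42–49% | 0 |

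*Beta-distributed personal miss probability, intraclass correlation 0.05 to 0.2.

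**What removal would do to the comparison.** Assumptions: no true effect, all controls kept, mean p = 0.10, logit of p linear in baseline with slope 0.5 or 1 per SD (poorer performers miss more), and baseline to week-12 correlation r = 0.5 or 0.7. Let δ be the mean baseline advantage of those kept, in SD. The week-12 comparison shifts by rδ and the change from baseline by −(1−r)δ, so the first minus the second equals δ. Simulated shifts (exercise minus control):

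| r | Slope | Week 12 | Change from baseline | δ |
|---|---|---|---|---|
| 0.5 | 0.5 | 0.078 | −0.079 | 0.157 |
| 0.5 | 1 | 0.131 | −0.130 | 0.261 |
| 0.7 | 0.5 | 0.109 | −0.048 | 0.157 |
| 0.7 | 1 | 0.183 | −0.078 | 0.261 |

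At slope 0 both shifts are zero to within simulation error. If better performers miss more, every sign reverses.

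**Scale.** With 12 controls and about 11 in an exercise arm, the standard error of a week-12 difference is √(1/12 + 1/11) = 0.42 SD.

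**The plan's loss allowance.** Sample size adds three per group: (9 + 3) × 3 = 36, which reproduces. Up to three losses per group leaves the 9 per group on which the stated 95% power is based.

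**The case against.** The best defence is that the exclusion rules only end participation, and that Statistical Treatment then says how such people are handled. On that reading the two sections are compatible, and intention to treat itself names the set: everyone, as randomised. This has force. A reader might infer that the protocol commits to dropping poor attenders from the analysis, and the documents do not establish that. But they do not state the milder reading either, the wording about exclusion from the study is strong, and under either reading the missing values have no method.

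It can also be said that the bias figures are hypothetical and less than half of one standard error. That is right. The miss rates, slopes and correlations are all assumed. The 15% and 20% rows in particular have no basis in the documents.

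Finally, the allowance of three extra per group might be thought to deal with losses. It protects numbers, and no loss of power is claimed here. It does not protect comparability between the arms.

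**Conclusion.** The point holds as a gap in the plan and a conflict to be reconciled, and it should be fixed before data are seen. What is certain is textual: no missing-data method supports the intention-to-treat promise, and the exclusion rules as worded remove randomised people, with the session rules reaching only the exercise arms.

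The size and direction of any bias are unknown. Under the assumptions above, applying the session rules to the analysis set moves the week-12 comparison by about 0.08 to 0.18 SD. It moves the baseline-to-week-12 change by about 0.05 to 0.13 SD in the opposite direction.

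Three stronger readings are not supported:

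- That the exclusions would flatter training. The planned main test is the time x group interaction, to which the change from baseline is closer. When poorer performers miss more sessions, that change shifts against training while the week-12 comparison shifts towards it.
- That loss after week 8 would bias the result by about 0.17 SD. That figure arises only for the week-12 comparison, at r = 0.7, the steepest slope tried (2 per SD of the week-8 value) and 25% versus 5% loss. At equal loss the shift is within 0.004 of zero, and the only allowance in the protocol is equal across groups.
- That a mixed model is always the less biased choice. In the same 25% versus 5% scenario, for an outcome with no week-8 value, the completer change was within 0.002 of zero, while a baseline-adjusted contrast was off by 0.020 to 0.064 SD.

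**What to change.** 1. Reconcile Eligibility criteria with Statistical Treatment. State that all randomised participants are analysed in their allocated group, and that the attendance and evaluation rules define only a secondary per-protocol set. Say what exclusion means in practice, and still invite people who miss sessions to the scheduled week-8 and week-12 assessments.
2. Replace the complete-case ANOVA with a method that keeps everyone with observed data. Two options are a likelihood-based mixed model (SPSS MIXED) for outcomes measured at baseline, week 8 and week 12, or stated multiple imputation within the planned ANOVA. Keep a multiplicity adjustment for the pairwise group contrasts; nothing here requires moving away from Tukey.
3. State the missing-at-random assumption. Note that for outcomes without a week-8 value the model may be no less biased than a completer change analysis. Report losses, exclusions and reasons by arm.

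The cost is a few sentences in two sections, slightly more analysis, and follow-up of people who stop training at visits already scheduled.
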